## 64 Study design

65 This study will emulate an investigator-initiated, pragmatic, multicentre, two-arm, open-label, 66 randomised, superiority treatment strategy trial in gout patients initiating ULT for the first time using 67 a cloning, censoring, and weighting approach [11]. Cloning is used to assign people to treatment 68 duration strategies at time zero (i.e., at ULT initiation), eliminating immortal time bias and creating 69 two identical study arms at baseline. Then, a clone is censored when their available data (i.e., the 70 serum urate levels) are no longer compatible with the treatment strategy of the arm they entered, 71 but the follow-up continues for that individual in the arm of the compatible strategy. This induces 72 informative censoring [12], which will be addressed using inverse probability weighting [13].

- The emulation of target trials using real-world data can lead to high-quality evidence and high concordance with randomised controlled trials when closer emulation of trial design and measurements is adopted [14].
- 76

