## 157 Covariates

- We will collect the following covariates ascertained on or before ULT initiation to build the inverseprobability of censoring weighting as detailed above:
- demographics: age, sex (male or female), latest body mass index (BMI) available only in CPRD,
   socioeconomic deprivation assessed using the index of multiple deprivation (IMD) at patient
- socioeconomic deprivation assessed using the index of multiple deprivation (IMD) at patient
   level in CPRD and income and educational level in VEGA, latest smoking status (current, past, or
- non-smoker) available only in CPRD, latest alcohol intake (current, past, or no intake) available
   only in CPRD. Demographic variables will be ascertained within the 5 years before ULT initiation,
- 165 gout-related variables: gout duration (years), presence of subcutaneous tophi, number of anti-
- 166 inflammatory prescriptions (colchicine, NSAIDs, and corticosteroids) in 12 months before ULT
- 167 initiation, number of consultations in primary care for gout and number of hospitalisations for

- gout in the 12 months before ULT initiation, ULT molecule (i.e., febuxostat, allopurinol,
   uricosurics) and dose (high vs low starting dose), co-prescription of gout flare prophylaxis with
   colchicine and/or non-steroidal anti-inflammatory drugs on the date of ULT initiation (i.e.,
   prescription length ≥21 days);
- 172 general health and other cardiovascular comorbidities: Charlson Comorbidity Index [28], 173 cardiovascular comorbidities not included in the Charlson Comorbidity index (i.e., hypertension, 174 atrial fibrillation, and hypercholesterolemia), heart failure, diabetes with and without target 175 organ damage, chronic kidney disease (stage 3,4,5), dementia, peripheral vascular disease, 176 COPD, cancer, HIV/AIDS European Society of Cardiology cardiovascular risk (high/very high vs 177 moderate/low), history of cardiovascular events before ULT initiation, number of consultations 178 in primary care for any reason and number of hospitalisations for any cause in the 12 months 179 before ULT initiation,
- 180 medications (low-dose acetylsalicylic acid (ASA), non-ASA antiplatelet agents, statins, fibrates,
- other lipid-lowering agents, potassium-sparing diuretics, thiazides, loop diuretics, beta-blockers,
   calcium-channel blockers, angiotensin-converting enzyme inhibitors and angiotensin receptor

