### 188 Statistical analysis

- 189 All descriptive statistics will be reported as number (percentage), mean (standard deviation (SD), or
- 190 median (interquartile range (IQR)) as appropriate.
- 191 Although cloning allows us to account for observed confounding at baseline, the artificial censoring 192 introduced is usually informative [12]. The proposed approach to address this problem is to use 193 inverse probability of censoring weighting. The purpose of the weights is to up-weight patients 194 remaining adherent to the protocol so that they represent censored patients, and as such, maintain 195 the comparability of the study arms throughout the grace period. Survival curves will be estimated 196 using a non-parametric Kaplan-Meier estimator weighted for the inverse probability of censoring 197 weights. The 95% confidence intervals for the difference in 5-year survival and the difference in 198 restricted mean survival times will be obtained using a non-parametric bootstrap with 1000 199 replicates [29].
- 200 First, data from Sweden and the UK will be analysed separately. Then, results will be meta-analysed.
- 201 All analyses will be performed using Stata, version 18 (StataCorp, Texas, USA).

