## 202 Inverse probability of censoring weighing

- In this study, we will estimate the inverse probability of censoring weights by fitting a pooled logistic
   model for the monthly probability of remaining uncensored, including variables for time (in its linear
- and/or quadratic terms depending on the data structure) and the baseline covariates. To avoid
  undue influence of outliers, weights will be truncated at the 99.5th percentile in case of extreme
  weights.
- 208 The inverse probability of censoring weighting will be built using two different models including a
- 209 different set of covariates as shown in the following table.

Variables	Model 1	Model
Age	Y	Y
Sex (male vs female)	Y	Y
Body Mass Index	N	Y
Socioeconomic deprivation	Y	Y
Smoking status	N	Y
Alcohol intake	N	Y
Gout duration (years)	Y	Y
Subcutaneous tophi (y/n)	Y	Y
Number of anti-inflammatory prescriptions (colchicine, NSAIDs, and corticosteroids) in	Y	Y
12 months before ULT initiation		
Number of consultations in primary care for gout and number of hospitalisations for	Y	Y
gout in the 12 months before ULT initiation		
ULT molecule (i.e., febuxostat, allopurinol, uricosurics)	Y	Y
ULT dose (high vs low starting dose)	Y	Y
Co-prescription of gout flare prophylaxis with colchicine and/or non-steroidal anti-	Y	Y
inflammatory drugs on the date of ULT initiation (i.e., prescription length ≥21 days)		
Charlson comorbidity index	N	Y
Cardiovascular comorbidities not included in the Charlson Comorbidity index (i.e.,	Y	Y
hypertension, atrial fibrillation, and hypercholesterolemia)		
Acute or chronic ischaemic heart disease, heart failure, diabetes with and without	Y	Y
target organ damage, chronic kidney disease (stage 3,4,5), dementia, peripheral		
vascular disease, COPD, cancer, HIV/AIDS		
History of cardiovascular events before ULT initiation	Y	Y
European Society of Cardiology cardiovascular risk	Y	Y
Number of consultations in primary care for any reason and number of hospitalisations	Y	Y
for any cause in the 12 months before ULT initiation		
Proportion of days covered by ULT between the date of ULT initiation and the end of	Y	Y
the grace period		N N
Low-dose ASA	Y	Y
Non-ASA antiplatelet agents	Y	Y
Statins	Y	Y
Fibrates	Y	Y
Other lipid-lowering agents	Y Y	Y
Potassium-sparing diuretics	Y Y	Y
Thiazides		Y
Loop diuretics	Y	Y
Beta-blockers	Y Y	Y
Calcium-channel blockers	Y Y	Y
Angiotensin-converting enzyme inhibitors	Y Y	Y
Angiotensin receptor blockers		Y
Other anti-hypertensive agents	Y	Y
Nitrates	Y	Y

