Ves, N: no.	Y	Y

211

212 Model 1 will be used to meta-analyse the results from CPRD and VEGA datasets. Model 2 will be

213 used to test the internal validity of the association between exposure and outcome and to check

whether the variables available only in CPRD could represent major confounders.

215 Missing data

216 BMI, smoking status, alcohol intake status, and socioeconomic deprivation can have missing data in

217 CPRD. The pattern of missingness will be compared and missingness at random assumed. Missing

- 218 data will be imputed using chained equations. BMI, smoking status, alcohol intake status, and
- 219 socioeconomic deprivation will be modelled using multinomial logistic regression.
- 220 Subgroup analyses
- 221 We will perform some sensitivity analyses to test the robustness of the association between the 222 exposure and the outcome.
- We will consider a SU target of ≤300 micromol/l to define the T2T-ULT arm and we will compare
   it with not achieving a SU target of ≤360 micromol/l,
- 225 We will further censor the follow-up when people will discontinue ULT,
- We will exclude from the FAF-ULT arm, those patients who will not have measured serum urate
   levels within 12 months after ULT initiation.
- 228 Also, we will stratify the analyses using the following prognostic factors:
- 229 Age (>65 and ≤65 years),
- 230 Gender (male and female).
- 231 Feasibility count and sample size considerations
- 232 In a previous study, we identified 96,000 patients with incident gout in CPRD. Of them, 48%

233 (~46,000) were ever prescribed ULT, and 28% (~12,000) and 16% (~7,000) achieved serum urate

- targets of  $\leq$ 360 micromol/l and  $\leq$ 300 micromol/l within 1 year after the first ULT prescription, respectively [2].
- 236 Approximately, 20,000 patients with an incident diagnosis of gout were ascertained in VEGA. Of
- them, 42% (~8,000) were prescribed ULT [30]. We assume a similar rate of success as in CPRD. Thus,
- data for approximately 14,000 exposed and 30,000 unexposed patients and 8,000 exposed and
- 239 30,000 unexposed patients will be available for the main aim and the secondary aim, respectively.
- Based on these data, our study will have more than 99% power to detect a risk difference of 1/1,000
- person-years assuming a rate of MACE of 17/1,000 person-years [5] in the unexposed and an alphaerror of 0.025.
- 243 Ethics, funding, and patient partner in research involvement

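### Both weight models pool colchicine with NSAIDs (and, in the prescription count, corticosteroids), so the weights do not target balance by agent: a low-cost refinement, not an error

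*Protocol*

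**What the plan says.** The table in the Protocol section on inverse probability of censoring weighting fixes the covariates of both weight models. Two rows describe anti-inflammatory treatment, each marked for Models 1 and 2:

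- Prophylaxis at ULT start: "Co-prescription of gout flare prophylaxis with colchicine and/or non-steroidal anti"-inflammatory drugs, with a prescription length of at least 21 days.
- Earlier use: "Number of anti-inflammatory prescriptions (colchicine, NSAIDs, and corticosteroids) in" the 12 months before ULT.

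The Covariates section groups them the same way: "inflammatory prescriptions (colchicine, NSAIDs, and corticosteroids) in 12 months before ULT" initiation for the count, and "colchicine and/or non-steroidal anti-inflammatory drugs on the date of ULT initiation (i.e" for prophylaxis. Corticosteroids are in the count but not in the prophylaxis item.

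None of the three classes is in the separate medications list, which is split more finely, for example "other lipid-lowering agents, potassium-sparing diuretics, thiazides, loop diuretics, beta-blockers".

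On the role of the weights, Study design says that cloning gives "two identical study arms at baseline". Statistical analysis says that the weights are there to maintain "the comparability of the study arms throughout the grace period".

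**The concern.** Read naturally, the prophylaxis item is one yes/no flag and the prescription item is one number. A patient given NSAID prophylaxis and one given colchicine then have the same flag. Six NSAID prescriptions and six colchicine prescriptions give the same count.

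Cloning removes any difference in agent use at time zero. From then on, clones leave the FAF arm when they reach target, and clones leave the T2T arm at month 12 if they have not. If the choice of agent goes with reaching target, for instance because both reflect how a practice manages gout, the mix of agents can drift apart between the arms, and weights built on pooled variables do not aim to correct it. If the agents also differ in cardiovascular risk, the drift enters the MACE contrast.

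The planned checks are unlikely to show this. Model 2 has the same pooled rows as Model 1, so comparing the two says nothing about it. None of the listed sensitivity analyses changes these covariates. The negative control outcomes (acute bronchitis, cataract, appendicitis) are poorly suited to detecting an agent effect specific to myocardial infarction and stroke.

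**Working it through.** **Step 1: text.** The protocol gives no figure on this point, so there is none to reproduce. Comparing the Covariates section with the weight table confirms one and/or prophylaxis item and one prescription count, both in both models, and no agent-specific term elsewhere.

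**Step 2: when bias arises.** Cloning makes agent use identical at baseline, so pooling alone creates no bias. It needs (a) a difference between agents in MACE risk and (b) an association of agent with reaching target, conditional on the other covariates.

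**Step 3: possible size.** Let p be the share of patients with the flag, c1 and c0 the colchicine share among flagged patients in the T2T and FAF arms after weighting, and Hc and Hn the MACE hazard ratios of colchicine and NSAID against no prophylaxis. All of these are assumed; the protocol gives none. Then

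spurious ratio = [1 − p + p(c1·Hc + (1 − c1)·Hn)] / [1 − p + p(c0·Hc + (1 − c0)·Hn)]

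The shift is 17 × (ratio − 1) per 1,000 person-years, where 17 is the protocol's MACE rate in the unexposed. The benchmark is the protocol's difference of 1 per 1,000 person-years, a ratio of 16/17 = 0.941. It serves here only as a yardstick.

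| p | c1 / c0 | Hc / Hn | Ratio | Shift per 1,000 PY |
|---|---|---|---|---|
| any | equal | any | 1.000 | 0 |
| 0.10 | 0.60 / 0.40 | 0.8 / 1.3 | 1.000/1.010 = 0.990 | −0.17 |
| 0.20 | 0.60 / 0.40 | 0.8 / 1.3 | 1.000/1.020 = 0.980 | −0.33 |
| 0.20 | 0.70 / 0.30 | 0.7 / 1.5 | 0.988/1.052 = 0.939 | −1.03 |
| 0.40 | 0.70 / 0.30 | 0.7 / 1.5 | 0.976/1.104 = 0.884 | −1.97 |

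The last row is the extreme of the grid examined (p 0.05 to 0.40, shares 50/50 to 70/30, hazard ratios 0.9/1.1 to 0.7/1.5). Swapping the mix in the third row gives 1.020/1.000 = 1.020, or 17 × 0.020 = +0.34, so the sign depends wholly on which arm has more colchicine.

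**Step 4: timing.** The table applies one contrast to all of follow-up, which overstates the first year. Take a second set of assumptions: a MACE rate ratio of 0.75 for colchicine against NSAID, and a colchicine share among flagged patients of 80% in those who reach target and 60% in those who do not.

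- *After month 12:* (0.80 × 0.75 + 0.20)/(0.60 × 0.75 + 0.40) = 0.80/0.85 = 0.941. That is 17 × 0.059 = 1.0 per 1,000 person-years among flagged patients, or 0.10 to 0.30 overall if 10% to 30% are flagged.
- *Months 0 to 12:* under Follow up, no T2T clone is artificially censored before month 12, so that arm is still the whole cohort. With the protocol's 28% reaching target, its colchicine share is 0.28 × 80% + 0.72 × 60% = 65.6%. The ratio is (0.656 × 0.75 + 0.344)/0.85 = 0.836/0.85 = 0.984. That is 0.28 per 1,000 among flagged patients, or 0.03 to 0.08 overall. Even this is an upper end, because FAF falls to 60% only once all who reach target have been censored.

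**The case against.** The strongest reply is that this is covariate coding and contradicts nothing in the protocol. Both items sit under gout-related variables, where a pooled count is a defensible measure of treatment burden, so the finer split of the cardiovascular drugs does not by itself show an inconsistency. Some table rows plainly bundle separate variables (gout consultations with hospitalisations; a run of comorbidities), so one row need not mean one model term. Both models also contain chronic kidney disease, heart failure, ischaemic heart disease, earlier cardiovascular events, ESC risk, and ULT molecule and dose. Agent choice explained by these is already handled. All of this stands, and it keeps the point from being an error.

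Four stronger readings are tempting, and the protocol does not support them:

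- *That the agents have opposite cardiovascular effects.* The protocol nowhere says so. Its negative control text names colchicine prophylaxis as the treatment of interest, but that says nothing about its effect relative to NSAIDs.
- *That agent use cannot be balanced.* It is balanced at time zero and may be balanced in part through the other covariates. It is only not targeted.
- *That the bias favours T2T.* This needs an assumption about which arm keeps more colchicine; the reverse mix reverses the sign.
- *That a shift of 1.0 per 1,000 among flagged patients applies throughout.* It cannot hold in the first 12 months. Beyond them it needs a prescription recorded on the ULT start date to mark a lasting difference, and the 80/60 mix to remain after weighting.

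What survives is that the wording most naturally means one flag and one count, and that nothing else in the models identifies the agent.

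**Conclusion.** An optional improvement, not a flaw that undermines the plan. As written, the weights do not target balance in which anti-inflammatory agent was used after artificial censoring. Whether confounding results is unknown, and so is its direction. Under moderate assumptions it is small, from zero to roughly 0.3 per 1,000 person-years, up to about a third of the benchmark difference of 1 per 1,000. It reaches or exceeds the benchmark only when a high prevalence of prophylaxis, a large residual difference in mix and strong opposite effects coincide. Prevalence, mix and agent effects are all assumed.

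**What to change.** In the Covariates section and in the weight table, for Models 1 and 2:

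1. Replace the prophylaxis flag with two indicators, colchicine and NSAID, keeping the existing date and prescription-length definition.
2. Replace the prescription count with three counts (colchicine, NSAIDs, corticosteroids) over the same 12 months.
3. Report each of the five variables by arm, before and after weighting.

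If separate coding was intended all along, items 1 and 2 only clarify the wording.

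The cost is slight. The prescriptions must already be identified by drug to build the pooled items. Two terms become five, three more parameters in models fitted to about 14,000 + 30,000 = 44,000 patients. No new data are needed and no clinical rule changes.

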- 51 healthcare-seeking behaviour biases may have affected the results [7,8]. Thirdly, no attempts were
- 52 made to ascertain whether the ULT initiators met the serum urate treatment target in all but one of 53 these studies [7–9].
- 54 A recent randomised controlled trial, the ALL-HEART study, showed that allopurinol does not 55 improve cardiovascular outcomes in patients with ischaemic heart disease, but gout was an 56 exclusion criterion for this study [10].
- 57

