## 77 Study setting and data source

78 This study will be carried out in England and Sweden using data recorded in the course of routine

- 79 clinical care for people with gout managed in primary care. General Practices contributing to the
- 80 Clinical Practice Research Datalink (CPRD) Aurum and the Western Sweden Regional Healthcare
- 81 Database (VEGA) will be included in the study.
- 82 We will extract CPRD data for the period between 01/01/2007 and 29/03/2021 and VEGA data for
- 83 the period between 01/01/2007 and 31/12/2017 covering the periods over which linkage with

secondary-care data will be available. Indeed, the first recommendations for the management of
gout by the BSR and the EULAR were published in 2007 and 2006, respectively [15,16].

86 • Clinical Practice Research Datalink Aurum

CPRD database includes information from more than 38 million individuals, representative of the English population in terms of age, sex, and ethnicity [17]. CPRD data include information on demographic characteristics, lifestyle factors, diagnoses, primary care prescriptions, laboratory results, and immunisations [17]. Primary care data are linked to patient-level index of multiple deprivation (IMD) scores, hospitalization records via linkage with the Hospital Episode Statistics (HES) dataset, and information on date and causes of death via linkage with the Office for National Statistics (ONS) dataset.

Western Swedish Health Care Register

VEGA contains information about all healthcare contacts for both primary and secondary healthcare
 in western Sweden (~1.7 million inhabitants). All diagnoses given by physicians are registered
 according to the Swedish version of the International Classification of Disease (ICD) 10 codes.

98

94

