## 110 Treatment strategies

- 111 Intervention arm (T2T-ULT arm): To emulate ULT initiation aiming to achieve the serum urate target
- 112 of  $\leq$  360 micromol/l within 12 months after ULT initiation, serum urate target will be ascertained by
- 113 the earliest recorded serum urate measurement  $\leq$ 360 micromol/l within 12 months after ULT 114 initiation.
- 115 *Comparison arm (FAF-ULT arm):* Emulation of ULT initiation without an aim to achieve a serum urate
- 116 target will use patients without any recorded serum urate measurements or with serum urate >360
- 117 micromol/l within 12 months after ULT initiation.
- 118 Previous randomised controlled trials showed that the serum urate target can be achieved within 6
- 119 months from the first ULT prescription [1,22,23]. However, the proportion of patients achieving the
- 120 serum urate target in clinical practice is expected to be lower [2]. Therefore, we will allow 12 months
- 121 of grace after ULT initiation for participants to achieve the serum urate target.
- 122

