### 148 Follow up

- 149 People will be followed up from the first ULT prescription to the earliest date of a cardiovascular
- event, transfer out of the primary-care practice, death, 5 years from the first ULT prescription, studyend, and last consultation in primary care.
- Artificial censoring will be applied as follows: 1) clones assigned to the T2T-ULT arm will be censored at 12 months from ULT initiation if they do not achieve the serum urate target, 2) clones assigned to the FAF-ULT arm will be censored at the time they achieve the serum urate target within 12
- 154 to the FAF-OLT and will be censored at the time they achieve the seruin drate target v
- 155 months after the first ULT prescription.
- 156

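### Being tested for urate helps decide which clones are censored, yet neither weight model includes how often urate was tested before ULT

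*Protocol*

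**What the plan says.** Protocol, Treatment strategies: T2T status is fixed by "the earliest recorded serum urate measurement" at or below 360 micromol/l within 12 months of starting ULT. The FAF arm without a urate "target will use patients without any recorded serum urate measurements or with serum urate >360" micromol/l. A patient who is never tested is therefore FAF, whatever the true urate.

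Protocol, Follow up: T2T clones are artificially censored "at 12 months from ULT initiation if they do not achieve the serum urate target". FAF clones are censored when a value at target is recorded within those 12 months.

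Protocol, Inverse probability of censoring weighing: both models include "Number of consultations in primary care for any reason and number of hospitalisations" and "Number of consultations in primary care for gout and number of hospitalisations for" gout, in each case over the 12 months before ULT. Both also include flare prophylaxis, statins, other lipid-lowering agents, low-dose ASA, antihypertensives and a long list of comorbidities. Adherence to ULT enters as "Proportion of days covered by ULT between the date of ULT initiation and the end of" the grace period, which is measured after baseline. No row counts earlier urate tests, and none records vaccination or screening.

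Protocol, Study setting and data source: CPRD holds "diagnoses, primary care prescriptions, laboratory results, and immunisations". Urate results must be available in both databases, because eligibility and the arm definitions depend on them.

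**The concern.** The weights can restore comparability after artificial censoring only for those determinants of censoring that they contain. Whether and how often urate is tested is a direct determinant. With no test there is no route into T2T, and each further test is another chance of a qualifying value. Patients monitored closely before ULT are likely to be tested more afterwards. If such patients also differ in MACE risk in ways the listed covariates miss, the two weighted arms will differ in risk even if reaching target does nothing.

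The effect sought is small, 1 per 1,000 person-years against 17, a rate ratio of 16/17 = 0.941, so modest residual confounding matters. The protocol is alert to this kind of problem. In its Background it says of earlier observational work that "healthcare-seeking behaviour biases may have affected the results".

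**Working it through.** **Does the gap exist?** Setting the arm definitions and censoring rules beside the weight table shows that it does. Testing determines censoring in both arms, and no baseline testing variable is listed. The eligibility criteria require a urate above 360 micromol/l before ULT, so everyone has at least one earlier test. No time window is attached to that test, and the number of tests in the prior 12 months can still vary.

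**How large could the bias be?** The protocol gives no figure for this, so there is none to reproduce. What follows is an illustration.

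Inputs from the protocol (Feasibility count and sample size considerations): 28% reach target within a year in CPRD; MACE rate 17 per 1,000 person-years in the unexposed; difference sought 1 per 1,000. From Follow up: no artificial censoring of T2T clones before month 12.

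Assumed inputs: a binary care-seeking trait in 50% of patients; odds ratio 1.5 to 3 for a recorded value at target; MACE rate ratio g of 0.9 to 0.7 in those with the trait; attainment linear over year 1; equal weight for each of 5 years; no adjustment by the existing covariates; no true effect.

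Central case, odds ratio 2 and g = 0.8:

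1. Probabilities of reaching target with the trait (p1) and without it (p0) solve 0.5(p1 + p0) = 0.28 at odds ratio 2. This gives p1 = 0.349 and p0 = 0.211.
2. Trait share among those reaching target: a = 0.349/0.560 = 0.623. Among those not reaching it: b = 0.651/1.440 = 0.452.
3. Years 2 to 5: ratio = [1 + a(g − 1)]/[1 + b(g − 1)] = 0.8754/0.9096 = 0.962. Difference = 17 × (1 − 0.962), which is 0.64 per 1,000 before rounding the ratio.
4. Year 1: the T2T arm still holds every clone, so its trait share is 0.50. The FAF share at time t (in years) is (1 − p1·t)/(2 − 0.56t), which falls from 0.50 to 0.452 and averages 0.479. Ratio = 0.900/(1 − 0.2 × 0.479) = 0.995. Difference = 0.08 per 1,000.
5. Five-year average: (0.08 + 4 × 0.64)/5 = 0.53 per 1,000 person-years.

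The same steps across the assumed range:

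| Odds ratio | g | a | b | Year 1 | Years 2 to 5 | 5-year average |
|---|---|---|---|---|---|---|
| 1.5 | 0.9 | 0.573 | 0.472 | 0.02 | 0.18 | 0.15 |
| 2 | 0.8 | 0.623 | 0.452 | 0.08 | 0.64 | 0.53 |
| 3 | 0.7 | 0.690 | 0.426 | 0.19 | 1.54 | 1.27 |

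Differences are per 1,000 person-years. If the trait went with higher MACE risk (g above 1), the same formulas would give a ratio above 1 and the bias would run against T2T.

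**The case against.** The case against has real force.

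- **Existing covariates.** A reader might infer that preventive care is absent from the models. It is not: statins, low-dose ASA, antihypertensives and flare prophylaxis are in both. Consultation counts enter alongside heart disease, diabetes, kidney disease, prior cardiovascular events and cardiovascular risk category. Given that measured illness, the remaining variation in consultations carries some information on care-seeking. This stands, and it means part of the bias is already removed. It does not close the gap, because these variables also reflect illness and drug indication, and none measures urate testing.
- **Planned safeguards.** One sensitivity analysis drops untested patients from the FAF arm, and three negative control outcomes are planned. Both bear on the problem. The first selects on testing after baseline and leaves differences in the number of tests. The second can reveal bias but not remove it. Neither changes the primary estimate.
- **The parallel with earlier studies.** A reader might infer that the protocol repeats exactly the bias it criticises. The earlier studies compared ULT users with non-initiators. Here everyone starts ULT and everyone has had a urate test, which narrows care-seeking differences. The same trait can still enter, by a different route.
- **Testing may track illness too.** Blood tests may be more frequent in sicker patients, so the direction of any bias is open. This stands. It is no argument against the covariate, since a baseline determinant of censoring related to MACE risk in either direction belongs in the weights.

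**Conclusion.** The point holds as a cheap improvement. A direct determinant of artificial censoring has no baseline counterpart in either weight model, and the listed covariates stand in for it only partly.

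A reader might go further and infer that the omission will produce an apparent T2T benefit. The documents do not support that: they give neither the strength nor the direction of the association between testing and MACE risk. A reader might also compare achievers with non-achievers over all five years and arrive at 0.64 per 1,000 (0.18 to 1.54). That ignores the fact that T2T clones are kept intact until month 12. Allowing for this, the illustration gives 0.53 per 1,000 person-years, range 0.15 to 1.27, against the 1 per 1,000 sought. Within each scenario it assumes no help from the existing covariates, so to the extent that they capture the trait the bias would be smaller. Only the 28%, the 17 per 1,000 and the censoring times come from the protocol. The figures show that the bias could matter, not that it is present.

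**What to change.** In the covariate list and the weight table, add to Models 1 and 2 the number of dates with a serum urate test in the 12 months before ULT initiation. Keep all existing covariates. Because Model 1 feeds the meta-analysis, this covariate would reach the pooled estimate.

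Add influenza vaccination in the 12 months before ULT to Model 2 only. Immunisations are described for CPRD but not for VEGA, and Model 2 exists to check whether variables available only in CPRD are major confounders, so it would serve as a check there.

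The cost is two derived covariates, a few lines of protocol text and slightly more variable weights. The urate results are already needed to apply the eligibility criteria and define the arms.

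### Model 2 adds the Charlson index as well as the three CPRD-only variables, so a change from Model 1 cannot be attributed to BMI, smoking and alcohol alone

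*Protocol*

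**What the plan says.** The Protocol section on inverse probability of censoring weighting sets out two covariate sets and gives each a use. For the first: "Model 1 will be used to meta-analyse the results from CPRD and VEGA datasets". The second is to test the internal validity of the association and to check "whether the variables available only in CPRD could represent major confounders".

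The model table in that section has these rows, absent from Model 1 and present in Model 2:

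- "Body Mass Index N Y"
- "Smoking status N Y"
- "Alcohol intake N Y"
- "Charlson comorbidity index N Y"

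The Covariates section states, item by item, which variables exist only in CPRD. BMI, smoking status and alcohol intake carry that label. The Charlson index is listed without it: "general health and other cardiovascular comorbidities: Charlson Comorbidity Index [28], 173 cardiovascular comorbidities not included in the Charlson Comorbidity index".

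On the Swedish source, the section on study setting and data source says: "VEGA contains information about all healthcare contacts for both primary and secondary healthcare". It adds that physicians' diagnoses are registered there in ICD-10.

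**The concern.** The comparison is meant to answer a specific question. VEGA has no BMI, smoking or alcohol data, so the pooled result must rest on weights without them. Fitting both models in CPRD should show whether that gap matters. For this, the models should differ in those variables and nothing else, but they also differ in the Charlson index.

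Two misreadings become possible. If the Charlson index moves the estimate, the movement may be put down to lifestyle factors and cast unwarranted doubt on the VEGA and pooled results. If the Charlson index and the lifestyle factors push in opposite directions, the estimate may stay still and lifestyle confounding may be reported as absent. Separately, the protocol gives no reason for leaving a collected baseline covariate out of the model used for pooling.

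**Working it through.** **Step 1: compare the two lists.** The protocol states no figure for this check, so the core of the matter is a row-by-row comparison.

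| Variable | Labelled CPRD-only (Covariates) | Model 1 | Model 2 |
|---|---|---|---|
| BMI | yes | N | Y |
| Smoking status | yes | N | Y |
| Alcohol intake | yes | N | Y |
| Charlson index | no | N | Y |

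Four rows differ and three are labelled CPRD-only, so 4 − 3 = 1 row, the Charlson index, is outside the stated question. These four rows are clear. Lower rows, from the proportion of days covered onward, are misaligned in the text copy available, so further differences cannot be excluded.

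**Step 2: what Charlson can add.** Both models already include ischaemic heart disease, heart failure, diabetes, chronic kidney disease, dementia, peripheral vascular disease, COPD, cancer, HIV/AIDS, hypertension, atrial fibrillation, hypercholesterolaemia, previous cardiovascular events, European Society of Cardiology risk, and counts of consultations and hospitalisations. Charlson contributes only its weighting and whatever the list leaves out. The documents do not say how strongly that remainder relates to reaching target or to MACE.

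**Step 3: an illustrative range.** Treat the remainder as one binary factor with prevalence p, odds ratio OR for reaching target and hazard ratio HR for MACE. Leaving it out shifts the rate difference by about

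shift = (p1 − p0) × r0 × (HR − 1), with r0 = 17 / (1 + p(HR − 1)) per 1,000 person-years.

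Here p1 and p0 are its prevalence in those who do and do not reach target. They are fixed by p, OR and the 28% reaching target. The 28% and the MACE rate of 17/1,000 are in the protocol's sample size section (the rate is given there for the unexposed and used here as the average). The values of p, OR and HR are assumptions.

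- *No association* (OR 1.0, HR 1.0): shift = 0.
- *Weak* (p 10%, OR 1.1, HR 1.2): p1 = 0.1063, p0 = 0.0976. r0 = 17/1.02 = 16.67. Shift = 0.0087 × 16.67 × 0.2 = 0.03 per 1,000.
- *Strong* (p 20%, OR 0.77, HR 1.5): p1 = 0.1710, p0 = 0.2113. r0 = 17/1.10 = 15.45. Shift = −0.0403 × 15.45 × 0.5 = −0.31 per 1,000.

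Against the difference of 1/1,000 person-years on which the study is sized, the shift runs from 0 through 3% to 31%, in either direction.

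**Step 4: compare with sampling error.** Of about 46,000 CPRD starters, 28% is 12,880, leaving 33,120. With five full years each, the unweighted standard error of the rate difference is √(0.017/64,400 + 0.017/165,600) = 0.00061, or 0.61 per 1,000. The 95% half-width is 1.96 × 0.6055 = 1.19 per 1,000. Shifts of 0.03 to 0.31 are about 3% to 26% of that.

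**The case against.** The best defence is that the authors regard the Charlson index as CPRD-only. The version they cite, reference 28, was adapted for Read/OXMIS coded databases, whereas VEGA uses ICD-10. On that reading the four rows are the CPRD-only set and only a label is missing. This is possible but unstated. It sits poorly with VEGA's full ICD-10 diagnoses, and with a Model 1 that already takes many individual comorbidities from VEGA. It would also still leave lifestyle and comorbidity burden mixed in one comparison.

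Second, Model 2 has another declared use, testing internal validity, and a fully adjusted model including Charlson suits that. This stands, but it does not make the contrast specific to the CPRD-only variables.

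Third, this is not the sole safeguard. The Outcomes section plans negative control outcomes (acute bronchitis, cataract, appendicitis) to detect uncontrolled confounding, and the two countries are analysed separately before pooling. This also stands. Negative controls cannot show whether BMI, smoking or alcohol is responsible, so the model comparison remains the check aimed at them.

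Fourth, offsetting can also occur among BMI, smoking and alcohol. That is true, and the fix does not remove it; it removes only the part due to Charlson.

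A reader might go further and infer that the pooled estimate is wrong, or that the check will usually mislead. The documents support neither. The comparison does not alter the pooled estimate. A high rate of false signals needs assumed strong residual effects and a formal 5% test of the difference between models. The protocol states no such test and asks only about major confounders.

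**Conclusion.** The stated purpose and the model table do not match: the comparison tests four variables jointly while being described as a test of the CPRD-only ones, of which the protocol names three. A change cannot be attributed to BMI, smoking and alcohol alone, and no change does not clear them.

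The consequence is probably modest and cannot be fixed from the documents. The illustrative 0 to 0.31 per 1,000 person-years depends wholly on assumed residual associations. It uses a simple point-exposure rate difference rather than the planned cloned and weighted survival estimates. If what Charlson adds is unrelated to reaching target or to MACE, there is no distortion. The point is worth correcting because it affects how a planned robustness check will be read and because the correction is cheap.

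**What to change.** In the model table, set the Charlson row to Y for Model 1, and state that the index is derived from ICD-10 diagnoses in VEGA and from the cited adaptation in CPRD. The four rows that now differ then reduce to BMI, smoking and alcohol.

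If the index cannot be derived in VEGA, label it CPRD-only in the Covariates section, add one CPRD run of Model 1 plus Charlson, and base the statement about BMI, smoking and alcohol on Model 2 versus that run. Model 2 can keep its internal-validity role unchanged.

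No new data are needed. The cost is one algorithm in VEGA or one extra model run, plus some overlap between Charlson and the itemised conditions, which Model 2 already accepts.
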